6.5 Protocol Discontinuation

If a subject decides to withdraw from the study (and not just from protocol therapy) all efforts should be made to complete the final study assessments. The site study team should contact the subject by telephone or through a clinic visit to determine the reason for the study withdrawal. If the reason for withdrawal is an adverse event, it will be recorded on the eCRF.

7. STUDY CALENDAR & EVALUATIONS: PHASE I DE-ESCALATION COHORT

Cycle = 28 days	Screen		Phase I De-escalation Cohort ² (±3 days)					Safety follow up ²	
	-90 days	-14 days ¹	Cycle 0 Day 1 (7 day cycle)	Cycle 1 Day 1	Cycle 1 Day 15	Cycle 2-4 Day 1	Cycle 7+ Q3 cycles ² (±4 wks)		
REQUIRED ASSESSMENTS									
Medical history, smoking history, trial awareness ⁵	X								
Diagnosis and Staging ⁶	X								
Physical exam, Vital signs, ECOG Performance status ⁷		X	X	X	X	X	X		X
AEs & concomitant medications		X	X	X	X	X	X		X
ECG	X								
LABORATORY ASSESSMENTS⁸									
Complete Blood Cell Count with diff (CBC)		X	X	X	X	X	X		X
Comprehensive Metabolic Profile (CMP) ⁹		X	X	X	X	X	X		X
HgA1C; LDH		X							X
Fasting glucose (if not part of CMP)		X	X	X	X	X	X		
Testosterone		X							X
Prostate specific antigen		X	X	X	X	X	X		X
Antibody studies for Hepatitis B, C and HIV	X								
DISEASE ASSESSMENT									
CT or MRI of chest, abdomen and pelvis	X					pre-C4	X ¹⁰		
Bone scan	X					pre-C4	X ¹⁰		
TREATMENT EXPOSURE									
Ipatasertib (once daily, continuous)			X	X	X	X			
Darolutamide (twice daily, continuous)				X ¹²	X	X	X		
Androgen deprivation therapy (per standard of care)			SOC	SOC	SOC	SOC	SOC		
CORRELATIVE STUDIES (SPECIMEN COLLECTION)									
Blood for somatic baseline			X						
Archival tissue slides, if available ¹¹	X								
Pharmacokinetic studies ¹²				X ¹²	X	C3			
Research blood/plasma collection			X	X		C2, C4			X
BANKING SAMPLES (SPECIMEN COLLECTION)									
Whole Blood and Unstained Slides (if available) ¹³				X					
Serum and Plasma				X					X

Key to Footnotes: Phase I De-escalation Cohort

¹If screening (baseline) labs were performed within 7 days of C1D1 of treatment, these do not need to be repeated.

²Visits should occur every 28 days. A window of 3 days will be applied to all treatment study visits; for safety follow-up visit a 7-day window will apply. Subjects will be seen every cycle through cycle 4 day 1, then may be seen every 12 weeks \pm 4 weeks (every 2-4 cycles) until documented disease progression or discontinue therapy.

³A safety follow-up visit will occur 30 days (\pm 7 days) after the last dose of treatment.

⁴Subjects without documented disease progression will be followed for disease progression every 6 months for 2 years.

⁵Medical history to include: smoking history, trial awareness question, prior ICH and genetic testing of tumor tissue.

⁶Diagnosis and staging to include pathology report and Tumor Node Metastasis (TNM) staging.

a. Staging may be captured from initial diagnosis.

b. Repeat abdominal imaging to confirm stage must be performed within 90 days of trial initiation.

c. Staging will be based on the 8th edition of the AJCC Cancer Staging Manual.

⁷Vital signs to include blood pressure, weight, and height (screening only) and ECOG performance status

⁸Laboratory assessment will be performed prior to treatment initiation as noted and every cycle thereafter at clinic visits during treatment periods.

⁹CMP to include sodium, potassium, chloride, creatinine, blood urea nitrogen; liver function tests (LFTs) to include AST, ALT, total bilirubin, alkaline phosphatase

¹⁰After Cycle 4, disease assessments will be performed every 12 weeks (+/- 4 weeks) for two years, and then every 16 weeks (+/- 8 weeks).

¹¹Fixed paraffin-embedded blocks/slides will be requested by the investigator enrolling the patient. Request should be placed when the patient is being screened and slides should be shipped by C1D1 of treatment. If available, slides are required for central confirmation of PTEN analysis and other biomarker research. See CLM for collection, labeling, and shipping instructions.

¹²Plasma will be collected on Cycle 1 Day 1 for Ipatasertib monotherapy PKs (pre-dose, +1h, +2h, +3h, +5h). Subjects will begin Darolutamide in the evening of C1D1 AFTER drawing samples for PKs on Ipatasertib. Additional samples will be collected on Cycle 1 Day 15 and Cycle 3 Day 1 (pre-dose, +1h, +2h, +3h, +5h on each day) to evaluate PKs for combination therapy.

¹³Submission of unstained slides for banking from an archived FFPE tumor block (if available). See CLM for collection, labeling, and shipping instructions.

STUDY CALENDAR & EVALUATIONS: PHASE II NEOADJUVANT COHORT

Cycle = 28 days	Screen		Phase II Neoadjuvant Cohort ² (± 3 days)			Surgery ³	Safety follow up ²	Long-term Follow up ⁵	
			Cycles 1-2		Cycles 3-6				
	-90 days	-14 days ¹	Day 1	Days 8, 15	Day 1	Day 29			
REQUIRED ASSESSMENTS									
Medical history, smoking history, trial awareness ⁶	X								
Diagnosis and Staging ⁷	X								
Physical exam, Vital signs, ECOG Performance status ⁸		X	X		X	X		X	
AEs & concomitant medications		X	X		X	X		X	
Immunohistochemistry for PTEN ¹¹	X								
ECG	X								
LABORATORY ASSESSMENTS⁹									
Complete Blood Cell Count with diff (CBC)		X	X		X	X		X	
Comprehensive Metabolic Profile (CMP) ¹⁰		X	X		X	X		X	
HgA1C		X				X		X	
Fasting glucose		X	X	X	X	X		X	
Testosterone; Prostate specific antigen		X	X		X	X		X	X
DISEASE ASSESSMENT									
CT or MRI of abdomen and pelvis	X								
Bone scan	X								
TREATMENT EXPOSURE									
Ipatasertib (once daily, continuous)			X	X	X				
Darolutamide (twice daily, continuous)			X	X	X				
Androgen deprivation therapy (per standard of care)			SOC	SOC	SOC				
CORRELATIVE STUDIES (SPECIMEN COLLECTION)									
Whole blood for somatic baseline			Pre-C1						
Archival biopsy slides ¹²	X								
Research blood/plasma collection ¹⁴			Pre-C1,C2			X			
Prostatectomy specimen							X		
BANKING SAMPLES (SPECIMEN COLLECTION)									
Whole Blood			Cycle 1						
Unstained Slides (if available)			Cycle 1				X		
Serum and Plasma			Cycle 1					X	
FOLLOW-UP									
Survival status, evidence of biochemical progression									X

Key to Footnotes: Phase II Neoadjuvant Cohort

¹If screening (baseline) labs were performed within 7 days of C1D1 of treatment, these do not need to be repeated.

²Visits should occur every 28 days. A window of 3 days will be applied to all treatment study visits; for safety follow-up visit a 7-day window will apply.

³Prostatectomy will occur within 28 days (± 14 days) of end of the sixth cycle.

⁴A safety follow-up visit will occur 30 days (± 7 days) after the last dose of treatment.

⁵Subjects without documented disease progression will be followed for disease progression every 6 months for 2 years.

⁶Medical history to include smoking history, trial awareness question prior IHC and genetic testing of tumor tissue.

⁷Diagnosis and staging to include pathology report and Tumor Node Metastasis (TNM) staging.

d. Staging may be captured from initial diagnosis.

e. Repeat abdominal imaging to confirm stage must be performed within 90 days of trial initiation.

f. Staging will be based on the 8th edition of the AJCC Cancer Staging Manual.

⁸Vital signs to include blood pressure, weight, and height (screening only) and ECOG performance status

⁹Laboratory assessment will be performed prior to treatment initiation as noted and every cycle thereafter at clinic visits during treatment periods. Following the conclusion of treatment, testosterone and PSA assessment will be continued with each visit during long term follow up at the interval noted above.

¹⁰CMP to include sodium, potassium, chloride, creatinine, blood urea nitrogen; liver function tests (LFTs) to include AST, ALT, total bilirubin, alkaline phosphatase

¹¹Immunohistochemistry for PTEN expression will be performed and evaluated by the enrolling institution for each patient and retrospectively undergo central review.

¹²Fixed paraffin-embedded blocks/slides will be requested by the investigator enrolling the patient. Request should be placed when the patient is being screened and slides should be shipped by C1D1 of treatment. Slides are requested for central confirmation of PTEN analysis and other biomarker research. See CLM for collection, labeling, and shipping instructions.

¹³Submission of unstained slides for banking from an archived FFPE tumor block (if available). See CLM for collection, labeling, and shipping instructions.

¹⁴Blood collected for biomarker evaluation (e.g. Immunogenicity and ctDNA).

7.1 Safety Follow-up Evaluations

A safety follow-up visit should occur when subjects permanently stop study treatment for whatever reason (toxicity, progression, or at discretion of site investigator) and should be performed 30 days (± 7 days) after the last dose of treatment. Subjects who have an ongoing \geq grade 2 or serious AE (SAE) at this visit will continue to be followed until the AE resolves to \leq Grade 1 or baseline, is deemed clinically insignificant, and/or until a new anti-cancer treatment starts, whichever is earlier.

7.2 Long Term Follow-up Evaluations

Subjects in the Phase I cohort will not have any long term follow-up evaluations.

All subjects in the Phase II neoadjuvant cohort will be followed every 6 months for two years following prostatectomy or until documented biochemical recurrence. If a subject does not undergo prostatectomy and does not have documented disease progression, he will be followed for disease progression every 6 months for 2 years. Follow up may be accomplished via clinic visit, phone call, or other avenues as appropriate. In cases of disease recurrence the choice of followup therapy will be as per the treating physician. However, adjuvant or salvage therapy should not start until after PSA and testosterone level results are obtained at least four weeks after surgery.

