9.1.2 Biochemical recurrence

Relapse or recurrence will be determined by detectable PSA (≥ 0.1 ng/mL) on scheduled bloodwork confirmed with a rising PSA at least one week later, the appearance of metastatic disease on imaging, or biopsy-proven relapse. For biochemical recurrence, the date of recurrence will be dated back to the initial detectable PSA.

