12.7.2 Phase II (Neoadjuvant Cohort)

In the Phase II neoadjuvant cohort, if after 9 evaluable patients there are no patients with exceptional response (defined as pCR or MRD), accrual will halt due to lack of efficacy. Accrual will not pause while the 9th patient is on therapy, so additional patients may accrue prior to pathologic evaluation of the 9th radical prostatectomy.

For the Phase II neoadjuvant cohort, an additional *early stopping rule for safety* will also be followed throughout the duration of the study. If, at any time, 2 or more patients experience a delay in time to prostatectomy of >28 days after the final dose of ipatasertib (i.e., a delay of > 1 week beyond the allowed timeline of 7-21 days) *due to an ipatasertib-related AE*, the study and all study treatment will be stopped. An ipatasertib-related AE is defined as an AE that is possibly, probably, or definitely related to ipatasertib. Should the study stop early, discussion of reopening the study using modified ipatasertib treatment regimens may be considered after discussion between the PI and Genentech, and after approval by the DSMC.

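### The post-operative PSA that section 7.2 relies on is not on the Phase II calendar, so a man who starts therapy on it before month 6 may never count as a biochemical recurrence

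*Combined protocol and SAP*

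**What the plan says.** - **Condition for further therapy (7.2).** "adjuvant or salvage therapy should not start until after PSA and testosterone level results are obtained at least four weeks after surgery".
- **Long-term follow-up (7.2).** Phase II men are "followed every 6 months for two years following prostatectomy or until documented biochemical recurrence". On the mode of contact: "Follow up may be accomplished via clinic visit, phone call, or other avenues as appropriate".
- **Calendar (Phase II).** The row "Testosterone; Prostate specific antigen" is marked at screening, Day 1 of each cycle, Day 29, safety follow-up and long-term follow-up. It is blank under surgery. Footnote 9 adds that after treatment "testosterone and PSA assessment will be continued with each visit during long term follow up at the interval noted above".
- **Safety visit (7.1; calendar footnote 4).** It "should be performed 30 days (± 7 days) after the last dose of treatment", so it is anchored to dosing and not to surgery.
- **Surgery.** Calendar footnote 3 gives 28 days, plus or minus 14, from the end of cycle 6. The stopping rule in 12.7.2 speaks of "a delay of > 1 week beyond the allowed timeline of 7-21 days" after the final ipatasertib dose.
- **Recurrence (9.1.2).** The PSA route is "detectable PSA (≥ 0.1 ng/mL) on scheduled bloodwork confirmed with a rising PSA at least one week later". Metastasis on imaging and biopsy-proven relapse also count. A biochemical recurrence is dated back to the first detectable PSA.
- **Endpoint and analysis (2.2.2, 12.2.2, 12.6.2).** Two-year biochemical recurrence-free survival is a secondary endpoint with a 0.2 ng/mL threshold, estimated by Kaplan-Meier. No rule covers therapy started before recurrence is confirmed.

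**The concern.** The protocol presumes a post-operative test that its calendar does not schedule, and its recurrence definition then admits only scheduled tests. The man most exposed is one whose PSA is detectable soon after surgery. Section 7.2 allows for him to have a PSA at four weeks or later and then be treated. That PSA is not on the schedule, and treatment can prevent the later rise that 9.1.2 requires. He can therefore fail biochemically and have no recorded event.

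Follow-up could also end for him. It runs until recurrence is documented, and a site might regard the unscheduled value as that documentation even though 9.1.2 records no event. He would then be censored at the point of failure. In a cohort of 17 to 20 men, a few such cases would visibly change the two-year estimate.

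**Working it through.** The plan gives no figure on this point to reproduce. The check is one of visit timing, followed by the effect of one misclassified man.

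**Timing inputs**, with day 0 as the last dose. I assume that all drugs end with cycle 6.
- Safety visit: 30 ± 7, so day 23 to 37 (7.1, footnote 4).
- Surgery: 28 ± 14, so day 14 to 42 (footnote 3); day 0 to 42 if the word 'within' in that footnote is read literally; day 7 to 21 (12.7.2).
- Required interval: at least 28 days after surgery (7.2).

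**Formula:** interval = safety-visit day − surgery day, over every whole-day pair.

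| Surgery window | Shortest | Longest | Pairs at 28 days or more |
|---|---|---|---|
| Day 14–42 | 23 − 42 = −19 | 37 − 14 = +23 | 0 of 29 × 15 = 435 |
| Day 7–21 | 23 − 21 = +2 | 37 − 7 = +30 | 6 of 15 × 15 = 225 (2.7%) |
| Day 0–42 | 23 − 42 = −19 | 37 − 0 = +37 | 55 of 43 × 15 = 645 (8.5%) |

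The six pairs in the second row need surgery on day 7, 8 or 9. The shares count day combinations and are not probabilities. At the nominal days (30 and 28) the safety draw falls 2 days after surgery. Under no window is a draw at four weeks assured. The next scheduled contact is month 6, and that may be a phone call.

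**Two men with detectable PSA at about week 4 to 6**
- *Untreated, PSA rising.* The month-6 draw is scheduled, detectable and can be confirmed. Section 9.1.2 does not require an earlier undetectable value, so he is an event by two years and the estimate shifts by 0 points. His event time may be late by about 26 − 4 = 22 weeks, or some 5 months.
- *Treated before month 6.* His first value was unscheduled, the confirming rise may not occur, and starting therapy is not itself an event. He may stay event-free in the data.

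**Effect of one man of the second kind**, with no other censoring before two years:
- Counted event-free: shift = 1/n. This is 1/17 = 5.9 points for the evaluable target and 1/20 = 5.0 points for planned enrolment.
- Censored at start of therapy, before d events in the other n − 1 men: shift = (d + 1)/n − d/(n − 1) = (1/n)(1 − d/(n − 1)), which is never more than 1/n.

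**The case against.** Much can be said for the plan.

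- **The pre-therapy PSA will exist.** Section 7.2 makes it a condition of further therapy, so in men managed to protocol there is a value at the site. This stands. It narrows the gap to whether that value is a study assessment and whether it counts.
- **The endpoint wording is broader than 9.1.2.** Sections 2.2.2 and 12.2.2 give a 0.2 ng/mL threshold with no reference to scheduled tests, so an unscheduled week-6 value above it is not plainly excluded. This also stands, but it leaves two definitions that can classify the same man differently.
- **These men fail elsewhere.** The PSA₀ endpoint in 2.2.2 and 12.2.2 excludes additional therapy, so they do not vanish from the results. That does not correct the recurrence-free estimate.
- **Footnote 9 already asks for PSA at each long-term visit.** True, but 7.2 lets the contact be by phone and does not say that a laboratory result is still needed.

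A reader might infer that persistent PSA escapes the endpoint altogether, or that the Kaplan-Meier curve cannot fall before month 6. The documents support neither. Untreated rising PSA is counted at month 6. Imaging or biopsy relapse can count at any time. A detectable safety-visit PSA taken after surgery is scheduled bloodwork, and 9.1.2 sets no four-week minimum for it. The back-dating rule is not limited to scheduled values either, so even some event times may be recovered.

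**Conclusion.** The gap is real and limited. Section 7.2 depends on a post-operative PSA and testosterone result that the Phase II calendar does not schedule, and month 6 is the first assured qualifying draw. Two-year biochemical recurrence-free survival is overstated only for men who start therapy on an unscheduled detectable PSA before month 6 and have no countable event afterwards. The size is about 5 to 6 points per such man, on the assumption that he is carried as event-free to two years.

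The total cannot be derived from the documents, because they give no rate of early PSA persistence or early therapy. If, purely as an assumption, 1 to 5 of 17 men were affected, the overstatement would run from 1/17 = 5.9 to 5/17 = 29.4 points if none of them were counted, and half that if half were counted. A reader should not take this range as an expected bias. For untreated rising PSA the two-year figure does not move. The primary endpoint and the two-stage decision rule are untouched.

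**What to change.** 1. Add a PSA and testosterone draw to the Phase II calendar and 7.2, in a post-operative window that opens at the four weeks already in 7.2, and collect it on the case report form.
2. State in 9.1.2 that this draw is scheduled bloodwork.
3. State in 9.1.2 and 12.6.2 that a detectable PSA followed by adjuvant or salvage therapy before the confirming value is an event, dated to that PSA. Add a sensitivity analysis that censors at the start of therapy. Without this step, step 2 alone would still lose men whose rise is prevented by treatment.
4. Require a laboratory PSA result when long-term follow-up is by phone.
5. Reconcile the two surgery windows (calendar footnote 3 and 12.7.2) and the two PSA thresholds (0.1 ng/mL in 9.1.2, 0.2 ng/mL in 2.2.2 and 12.2.2).

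These are measurement and analysis rules; none changes when a man is treated. The cost is one routine blood draw per man, a calendar column and a form page, and possibly a lower recurrence-free estimate. Sample size, type I error and power do not change.

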8. BIOSPECIMEN STUDIES AND PROCEDURES

The current study will collect pre-treatment and post-treatment archival tissue from diagnostic biopsy and radical prostatectomy, respectively, for use in exploratory studies. We hypothesize that co-inhibition of AR and AKT will cause an exceptional pathologic response in patients with prostate cancer with PTEN loss, but other pathways may contribute to resistance to this strategy. These include persistent activation of hormone receptors or the PI3K pathway despite inhibition, or differentiation toward neuroendocrine phenotype. In addition, PI3K pathway inhibition may release repression of immune pathways. Exploratory objectives of this study include evaluation for PI3K-AKT pathway activity and effects on other drivers of proliferation and survival (e.g. androgen receptor (AR), glucocorticoid receptor (GR), proliferation (using Ki-67) and change in neuroendocrine marker expression among others). See Correlative Laboratory Manual for detailed collection, processing, and shipping instructions.

8.1 Source and Timing of Biospecimen Collections

8.1.1 Phase I de-escalation cohort

Tissue – For the Phase I cohort, the most recent archival tissue available will be requested. This is mandatory if available, but patients may enroll if archival tissue is not available. If and when funding becomes available, these studies will include immunohistochemical (IHC) analysis (such as evaluation of expression of hormone receptors, markers of proliferation, neuroendocrine markers, and immune markers), as well as extraction and evaluation of DNA and RNA for genetic analysis.

Blood for Pharmacokinetics –

Plasma will be collected Cycle 1 Day 1, Cycle 1 Day 15 and Cycle 3 Day 1 (pre-dose, +1h, +2h, +3h, +5h on each day) to evaluate PKs. Plasma will be collected on Cycle 1 Day 1 for Ipatasertib monotherapy PKs (pre-dose, +1h, +2h, +3h, +5h). Subjects will begin Darolutamide in the evening

AFTER drawing samples for PKs on Ipatasertib. Additional samples will be collected on Cycle 1 Day 15 and Cycle 3 Day 1 (pre-dose, +1h, +2h, +3h, +5h on each day) to evaluate PKs for combination therapy.

Blood/plasma for immunogenicity studies and ctDNA - Blood will be collected Cycle 0 Day 1, Cycle 1 Day 1, Cycle 2 Day 1, Cycle 4 Day 1, and at safety follow up. Analysis to be performed upon receipt of funding.

Blood for somatic baseline - Whole blood will be collected prior to C1D1 treatment for somatic baseline comparison.

8.1.2 Phase II Neoadjuvant cohort

Prostate biopsy - Archival tissue must be available to evaluate for PTEN loss locally using the Ventana SP218 immunohistochemistry assay. Central review to confirm PTEN loss will be performed retrospectively. If and when funding becomes available, additional studies may include immunohistochemical (IHC) analysis (such as evaluation of expression of hormone receptors, markers of proliferation, and neuroendocrine markers), as well as extraction and evaluation of DNA and RNA for genetic analysis.

Prostatectomy specimen - Once the prostatectomy specimen has been evaluated for clinical purposes, tissue is required for central review and correlative studies. If there is more than minimal residual disease on a single block, a block representative of the residual disease is requested to be used for exploratory studies, as well as a corresponding H&E slide. If and when funding becomes available, these studies will include immunohistochemical (IHC) analysis (such as evaluation of expression of hormone receptors, markers of proliferation, neuroendocrine markers, and immune markers), as well as extraction and evaluation of DNA and RNA for genetic analysis. If there is a pathological complete response (pCR) or minimal residual disease (MRD) by local review, slides from each block are requested for central review.

Blood/plasma for immunogenicity studies and ctDNA - Blood will be collected Cycle 1 Day 1, Cycle 2 Day 1, and Cycle 6 Day 1. Analysis to be performed upon receipt of funding.

Blood for somatic baseline - Whole blood will be collected prior to C1D1 treatment for somatic baseline comparison.

